5.5.3 Highly Effective Methods of Contraception

Female subjects of childbearing potential who are sexually active with a non-sterilized male partner must agree to use at least one highly effective method of contraception from the time of screening and must agree to continue using such precautions for 180 days after the last dose of investigational product. Male partners of a female subject must also agree to use male condom plus spermicide throughout this period.

Non-sterilized male subjects who are sexually active with a female partner of childbearing potential must use male condom plus spermicide from screening through 180 days after the last dose of investigational product. Female partners of a male subject must use a highly effective

method of contraception throughout this period.

A highly effective method of contraception is defined as one that results in a low failure rate (i.e. less than 1% per year) when used consistently and correctly. Note that some contraception methods are **not** considered highly effective (e.g. male or female condom with or without spermicide; female cap, diaphragm, or sponge with or without spermicide; non-copper containing intrauterine device; progestogen-only oral hormonal contraceptive pills where inhibition of ovulation is not the primary mode of action [excluding Cerazette/desogestrel which is considered highly effective]; and triphasic combined oral contraceptive pills).

Table 2: Highly Effective ^a Methods of Contraception			
Barrier/Intrauterine Methods	Hormonal Methods		
 Copper T intrauterine device Levonorgesterel-releasing intrauterine system (eg, Mirena[®])^b 	 Etonogestrel implants: e.g. Implanon or Norplan Intravaginal device: e.g. ethinylestradiol and etonogestrel Medroxyprogesterone injection: e.g. Depo-Provera Normal and low dose combined oral contraceptive pill Norelgestromin/ethinylestradiol transdermal system Cerazette (desogestrel) 		
^a Highly effective (i.e. failure rate of $<1\%$ per year			

Highly effective (i.e. failure rate of <1% per year)

b This is also considered a hormonal method

5.6 Criteria for Taking a Participant Off Protocol Therapy

Duration of therapy will depend on individual response, evidence of disease progression and tolerance. In the absence of treatment delays due to adverse event(s), treatment may continue indefinitely as described in Section 5.2 or until one of the following criteria applies:

- Disease progression (exception for allowed retreatment as described in Section 5.2). •
- Intercurrent illness that prevents further administration of treatment •
- Unacceptable adverse event(s) •
- Participant demonstrates an inability or unwillingness to comply with the medication • regimen and/or documentation requirements
- Participant decides to withdraw from the protocol therapy
- General or specific changes in the participant's condition render the participant unacceptable for further treatment in the judgment of the treating investigator

Participants will be removed from the protocol therapy when any of these criteria apply. The reason for removal from protocol therapy, and the date the participant was removed, must be documented in the case report form (CRF). Alternative care options will be discussed with the participant.

The research team will update the relevant Off Treatment information in OnCore.

In the event of unusual or life-threatening complications, treating investigators must immediately notify the Overall PI, [name] at [contact].

5.7 Duration of Follow Up

Participants will be followed until death after removal from protocol therapy. This follow up will be performed by review of the medical record, contact with care providers, and/or telephone contact as needed every 3-4 months.

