1.3 Secondary Objectives

- Determine the progression free survival (PFS) rate, defined as the time from registration to disease progression or death due to any cause. Participants alive without disease progression will be censored at date of last disease evaluation.
- Determine the overall survival (OS) rate, defined as the time from registration to death due to any cause (or censored at date last known alive).
- Determine the duration of response (DoR), defined as the time from documentation of tumor response to disease progression (or censored at the date of last disease evaluation).
- Evaluate the safety and tolerability of tremelimumab in combination with durvalumab.

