Grade 1 or 2 AEs have been managed clinically without requiring dose modifications or delays. Treatment-related Grade 3 AEs have been manageable and reversible with standard toxicity management guidelines including steroids with the exception of 1 subject who experienced Grade 4 myasthenia gravis and polymyositis (with fatal outcome). This event was reported as an SAE (death).

Two subjects in the durvalumab 20 mg/kg plus tremelimumab 3 mg/kg Q4W cohort experienced DLTs. One subject had Grade 3 increased AST on Day 29 of Cycle 1; a second subject had Grade 3 increased amylase and Grade 4 increased lipase on Day 9 of Cycle 1.

A total of 56 subjects (54.9%) reported at least 1 SAE. Most commonly reported preferred terms (> 5%) were colitis (9.8%) and diarrhea (7.8%). SAEs that were not coded at the time of data cut-off were VTs of gastrohepatic mass resection, elective diagnostic surgical excision of cerebral lesion, neuromuscular disorder, progression of disease, progression of malignant neoplasm, and chest pain. The majority of subjects with SAEs (94.6%) had events of Grade 3 or higher severity. Thirty-six (35.3%) subjects experienced SAEs that were considered related to investigational products. Twenty-six subjects (25.5%) discontinued treatment due to SAEs of colitis (7 subjects); pneumonitis (5 subjects each); diarrhea (3 subjects); increased AST and dyspnea (2 subjects each); and pancreatitis, sepsis, increased ALT, arthralgia, malignant neoplasm progression, lung disorder, and NSCLC (1 subject each).

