2.5.2 Rationale for 4 Cycles of Combination Therapy Followed by Durvalumab Monotherapy

Long-term follow up on melanoma patients treated with ipilimumab, an anti-CTLA-4 targeting antibody (dosed every 3 weeks [q3w] for 4 doses and then discontinued), shows that patients responding to ipilimumab derive long-term benefit, with a 3-year OS rate of approximately 22%. Furthermore, the survival curve in this population reached a plateau at 3 years and was maintained through 10 years of follow up³².

Similar data have been presented for other anti-PD-1/PD-L1 targeting antibodies:

Nivolumab (anti-PD-1) was dosed q2w for up to 96 weeks in a large Phase I dose-escalation and expansion study, and showed responses were maintained for a median of 22.94 months for melanoma (doses 0.1 mg/kg to 10 mg/kg), 17 months for NSCLC (doses 1, 3, and 10 mg/kg), and 12.9 months for renal cell carcinoma patients (doses 1 and 10 mg/kg) at the time of data analysis³³⁻³⁵. Furthermore, responses were maintained beyond treatment discontinuation in the majority of patients who stopped nivolumab treatment (either due to protocol specified end of treatment, complete response [CR], or toxicity) for up to 56 weeks at the time of data analysis³⁶.

MPDL3280A (anti-PD-L1) was evaluated in a phase I study in which patients were dosed for a finite time period. Responses were maintained beyond treatment discontinuation³⁷. The same has been reported for combination therapy using nivolumab with ipilimumab²⁶.

Similar long term results may be expected with use of other immune-mediated cancer therapeutics including anti-CTLA-4 antibodies such as tremelimumab, anti PD-L1 antibodies such as durvalumab, or the combination of the two.

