5.2 Duration of Treatment and Criteria for Retreatment

Participants who are tolerating durvalumab monotherapy without evidence of disease progression per modified RECIST criteria for mesothelioma may continue to receive durvalumab as monotherapy indefinitely or until other criteria for discontinuation are met (see Section 5.6).

Participants experiencing either confirmed or unconfirmed PD during the durvalumab monotherapy portion of the trial may undergo retreatment with tremelimumab (once only) if they meet the retreatment criteria below. The same treatment guidelines followed during the initial treatment period will be followed during the retreatment period, including the same dose and frequency of treatments and the same schedule of assessments, with the exception that participants undergoing retreatment are not required to undergo additional tumor biopsies.

- 1. The patient has not received any other anticancer treatments for their disease (with the exception of palliative radiation or surgical procedures as allowed per protocol).
- 2. The patient does not meet any of the other investigational product discontinuation criteria (Section 5.6).
- 3. Absence of clinical symptoms or signs indicating clinically significant disease progression.
- 4. No decline in ECOG performance status compared to baseline.
- 5. Absence of rapid PD or threat to vital organs/critical anatomical sites (e.g., spinal cord compression) requiring urgent alternative medical intervention.
- 6. All AEs while receiving initial therapy must have resolved to ≤ Grade 1 or baseline. Must not have experienced a ≥ Grade 3 AE, or pneumonitis or neurologic AE of any grade while receiving initial therapy. Note: Subjects with an endocrine AE of any grade are permitted to be retreated if they are stably maintained on appropriate replacement therapy and are asymptomatic.
- 7. Must not have used additional immunosuppression other than corticosteroids for the management of an AE, must not have experienced recurrence of an AE if rechallenged, and not currently requiring maintenance doses > 10 mg prednisone or equivalent per day.
- 8. The patient has had a tumor imaging assessment within 28 days of restarting their assigned treatment; all further scans should occur with the same frequency as during the initial treatment period (relative to the date of registration) until study treatment is stopped.

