10. STUDY CALENDAR

Baseline evaluations are to be conducted within two weeks prior to start of protocol therapy, with the exception of the informed consent and baseline imaging which must be done ≤ 4 weeks prior to the start of therapy.

Assessments must be performed prior to administration of any study agent.

Table 7: Study Calendar									
	Pre- Study	Cycle 1 Day 1	Cycle 1 Day 15 ^H	Cycle 2 Day 1 ¹	Cycle 3 Day 1 ¹	Cycle 4 Day 1 ¹	Day 1 of Each Subsequent Cycle (after Cycle 4) ¹	Off Treatment ^J	Every 3 Months after Discontinuing ^K
Tremelimumab ^A		Х		Х	Х	Х			
Durvalumab ^A		Х		Х	Х	Х	Х		
Informed consent	Х								
Demographics	Х								
Medical history	Х								
Concurrent meds	Х		X				X	Х	
Tumor Biopsy ^B	Х			Х				Х	
Physical exam	Х	Х	Х	Х	Х	Х	Х	Х	
Vital signs ^C	Х	Х	Х	Х	Х	Х	Х	Х	
Height	Х								
Weight	Х	Х	Х	Х	Х	Х	Х	Х	
ECOG Performance status	Х		Х	Х	Х	Х	Х	Х	
CBC w/diff, plts	Х	Х	Х	Х	Х	Х	Х	Х	
Serum chemistry ^D	Х	Х	Х	Х	Х	Х	Х	Х	
Urinalysis (with microscopy)	Х								
EKG ^E	Х								
Serum β-hCG ^F	Х								
Adverse event evaluation	Х	ХХ					Х		
Tumor measurements	Х	Tumor measurements are repeated every 8 weeks, there is a ± 7 day window. Documentation (radiologic) must be provided for participants removed from study for progressive disease.				Х			
Radiologic evaluation	Х	CT or MRI imaging of any disease-involved site. Radiologic measurements should be performed every 8 weeks, there is a ± 7 day window.				Х			
Blood immune analysis ^G		Х		Х	Х		As indicated in footnote G.	Х	

Table 7: Study Calendar										
		Pre-	Cycle 1	Cycle 1 Day 15 ^H	Cycle 2 Day	Cycle 3 Day	Cycle 4 Day	Day 1 of Each Subsequent Cycle (after Cycle 4) ¹	Off Treatment ^J	Every 3 Months after Discontinuing ^K
		Study	Day 1	Day 15		_				 
-	or Care Provider									Х
Contact A.	As described in §									

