11. MEASUREMENT OF EFFECT

11.1 Antitumor Effect – Solid Tumors

For the purposes of this study, participants should be re-evaluated for response every 8 weeks. In addition to a baseline scan, confirmatory scans should also be obtained 8 weeks following initial documentation of objective response.

Response and progression will be evaluated in this study using the modified Response Evaluation Criteria in Solid Tumors (RECIST) guidelines for mesothelioma (version 1.1).⁴⁴

Tumor thickness perpendicular to the chest wall or mediastinum is measured in two positions at three separate levels on transverse cuts of a CT scan. The sum of the six measurements defines a pleural unidimensional measure. Transverse cuts at least 1 cm apart and related to anatomical landmarks in the thorax are chosen to allow reproducible assessment at later time points. If measureable tumor is present, transverse cuts in the upper thorax, above the level of division of the main bronchi are preferred. At reassessment, pleural thickness is measured at the same position at the same level. This is not necessarily the greatest tumor thickness at that level. Nodal, subcutaneous and other bidimensionally measurable lesions are measured unidimensionally as per the RECIST 1.1 criteria. Unidimensional measurements are added to obtain the total tumor measurement.

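### No scan is scheduled after a stop without progression, so PFS is censored early in survivors and dated late in those who die; the imaging text and the two DoR definitions need reconciling

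*Combined protocol and SAP*

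**What the plan says.** **Imaging on treatment.** Section 10, Table 7: "Radiologic measurements should be performed every 8 weeks, there is a ± 7 day window". Table 7 also appears to schedule one tumour assessment at the off-treatment visit. The only entry legible in its column for three-monthly follow-up after discontinuation is contact with the participant or care provider. Footnotes J and K are only partly legible in the text available; what can be read mentions no imaging.

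**Imaging after treatment.** Section 5.7 follows participants until death and names the means: "This follow up will be performed by review of the medical record, contact with care providers, and/or telephone contact as needed every 3-4 months". No scan is among them. Section 11.1 is worded differently: "participants should be re-evaluated for response every 8 weeks", with no stated end.

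**Leaving therapy without progression.** Section 5.6 allows this for intercurrent illness, unacceptable adverse events, non-compliance, withdrawal from therapy or investigator judgement.

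**Endpoints.** Sections 1.3 and 11.1.6 end PFS at progression or death from any cause. For everyone else, Section 1.3 says: "Participants alive without disease progression will be censored at date of last disease evaluation". DoR ends at progression alone in Section 1.3, but at progression or death in Section 11.1.5. Section 13.3 rules out imputation and assumes that data are missing at random. No rule covers death after a long interval without a scan.

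**The concern.** The PFS definition is conventional, but it presumes that progression is looked for until it occurs. If looking stops with treatment, two participants with the same unseen progression are recorded differently. One who stays alive is censored at the last scan; one who dies has an event at death, possibly months after the true progression. Whether a participant is censored then depends on the outcome, and Kaplan-Meier estimation assumes that it does not.

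The participants affected are not a random subset, since many will be toxicity stops. DoR has the same gap: a responder who stops early has either a truncated duration (Section 1.3) or one that may run to a late death (Section 11.1.5). Both are secondary endpoints.

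**Working it through.** **1. The plan's own figures.** The plan gives no power or precision for PFS or DoR. Its response-rate design reproduces. With 19 then 21 participants, continuing at 4 or more responses and declaring success at 10 or more of 40:

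- Early stopping under the null = P(X1 ≤ 3 | 19, 0.16) = 0.638 (stated 0.64).
- Type I error = Σ from x = 4 to 19 of P(X1 = x | 19, 0.16) × P(X2 ≥ 10 − x | 21, 0.16) = 0.082 (stated 0.08).
- Power, the same sum at 0.35, = 0.901 (stated 90%).
- Accrual: 40 / 5 per quarter = 8 quarters = 24 months; plus 12 months of follow-up = 36 months, as stated.

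Nothing below changes these figures.

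**2. Two invented participants.** Both stop at month 3 for toxicity with a clear off-treatment scan, and both progress at month 5. Eight weeks is 56 / 30.4375 = 1.84 months, so continued scanning would find progression at 3 × 1.84 = 5.52 months.

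- Participant A dies at month 11. PFS event at 11 months, which is 11 − 5.52 = 5.48 months late.
- Participant B is alive at cut-off. Censored at month 3, and the event is lost.
- If both had responded, Section 1.3 censors both DoRs at the month-3 scan. Section 11.1.5 runs A's to month 11 and censors B's at month 3.

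**3. Size, by simulation.** There were 400,000 participants per scenario, with uniform accrual over 24 months and cut-off at 36 months. Assumptions not in the documents: exponential times; median time to progression 3, 4 or 6 months; median survival after progression 4, 8 or 12 months; 25.5% or 40% of participants subject to a non-progression stop with a median of 2 months; no death before progression. Scanning every 8 weeks until progression is compared with no scan after stopping, where only death then counts and survivors are censored at the off-treatment scan. Ranges cover the six scenarios in each row.

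| Median time to progression | Stop before progression | 6-month PFS: full scanning → none after stop | Overstatement, points | 12-month PFS: full scanning → none after stop | Overstatement, points | Median delay of event in those who die |
|---|---|---|---|---|---|---|
| 3 months | 15.2-24.0% | 27.8-27.9% → 31.7-34.9% | 3.8-7.0 | 7.6-7.8% → 10.4-14.0% | 2.8-6.3 | 2.6-5.7 months |
| 4 months | 16.9-26.7% | 38.3-38.5% → 41.4-44.1% | 3.1-5.8 | 14.5-14.7% → 17.1-20.5% | 2.5-5.8 | 2.5-5.5 months |
| 6 months | 19.1-30.0% | 52.7-52.9% → 54.6-56.6% | 1.9-3.9 | 27.7-28.0% → 29.3-31.8% | 1.6-3.9 | 2.4-5.1 months |

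The Kaplan-Meier median was the same under both schedules (3.68, 5.52 and 7.36 months) because it sits on the 8-week scan grid. In participants, 15-30% of 40 is 6 to 12.

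**4. Against sampling error.** The half-width of a two-sided 80% interval, ignoring censoring, is 1.2816 × √(p(1 − p)/40). At p = 7.8% this is 5.4 points; at p = 27.7% it is 9.1 points. The worst-case bias is therefore comparable with the half-width in the first row and below half of it in the last.

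**5. The proxy for stopping.** Section 2.4.2 reports: "Twenty-six subjects (25.5%) discontinued treatment due to SAEs of colitis", followed by other terms. Applied here, 0.255 × 40 = 10.2 participants. The listed terms sum to 26 and include one neoplasm progression and one NSCLC. Without those two the figure is 24/102 = 23.5%.

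**The case against.** The best defence is that the plan does not forbid later scans. Section 11.1 sets 8-weekly re-evaluation without an end. The note under Table 8 asks sites to try to document progression after treatment ends. Section 5.7 requires record review every 3-4 months, which can surface routine scans. Section 6 lets some participants drop tremelimumab alone and remain on durvalumab, still being scanned. PFS and DoR are secondary, with no threshold to meet. This stands to the extent that the simulation is a worst case. It does not remove the gap. Section 11.1 conflicts with Section 5.7 and Table 7 rather than overriding them, the Table 8 note concerns symptomatic deterioration and sets no schedule, and nothing requires routine scans to be collected, read centrally or used to date progression.

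Three stronger readings are tempting and are not supported:

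- *That the plan orders imaging to end with treatment.* Section 5.2 does say "further scans should occur with the same frequency as during the initial treatment period (relative to the date of registration) until study treatment is stopped", but this is a condition for tremelimumab retreatment after progression, not a rule for those who stop without it.
- *That the plan cannot test its own rationale.* Section 2.5.2 cites findings that "responses were maintained beyond treatment discontinuation in the majority of patients" who stopped nivolumab. That section mainly supports ending tremelimumab after four cycles, while durvalumab and its 8-weekly scans continue.
- *That a quarter of participants will stop for toxicity.* The 25.5% pools ten NSCLC dose cohorts. Section 2.4.2 reports more discontinuations as tremelimumab rises above 1 mg/kg, and Section 2.5.1 equates this trial's 75 mg with 1 mg/kg. The figure is a rough proxy, probably high for this dose level.

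**Conclusion.** The point holds as a gap in follow-up and a conflict between passages. After a stop without progression, no tumour assessment is legibly scheduled beyond the off-treatment visit. PFS is then censored or dated late depending on whether the participant dies, and DoR after stopping is not systematically observed. The two DoR definitions also disagree on whether death is an event.

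The size rests on assumptions outside the documents. With 15-30% stopping before progression and no routine scan captured, PFS is overstated by roughly 2-7 points at 6 months and 2-6 points at 12 months. Any routine scans captured should reduce this. Every scenario run overstated PFS, but because survivors lose follow-up while deaths count, the direction could differ under other assumptions. A reader might infer that the main result is at risk. It is not: the response-rate decision rule is unaffected and median PFS barely moves. The change is worth making because it is cheap and because scans not collected during follow-up may be hard to recover later.

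**What to change.** 1. **Sections 5.7, 10 (Table 7) and 11.1:** reconcile these so that one statement says what tumour assessment applies after a stop without progression. At a minimum, in Section 5.7 and the Table 7 follow-up column, collect the routine-care scans found at the 3-4-monthly record review. Have the imaging core named in Section 11.1.7 read them, and use them to date progression until progression, new anticancer therapy or death.
2. **Sections 11.1.5, 11.1.6 and 13.3:** add a sensitivity analysis that censors PFS and DoR at the last disease evaluation when death occurs more than a stated interval after it, and report how many participants this affects. Two scan intervals plus the visit window would be 2 × 8 weeks + 7 days = 17 weeks. State it as elapsed time, because a rule based on missed visits has no meaning where none are scheduled.
3. **Sections 1.3 and 11.1.5:** use one DoR definition and say whether death is an event.

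Cost: central reading of a few existing scans and one extra analysis. No new participant procedure is needed, and sample size, type I error and power are unchanged.

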5.8 Criteria for Taking a Participant Off Study

Participants will be removed from study when any of the following criteria apply:

- Lost to follow-up
- Withdrawal of consent for data submission
- Death

The reason for taking a participant off study, and the date the participant was removed, must be documented in the case report form (CRF).

The research team will update the relevant Off Study information in OnCore.

6. DOSING DELAYS

Dose delays will be made as indicated in the following tables. The descriptions and grading scales found in the revised NCI Common Terminology Criteria for Adverse Events (CTCAE) version 4.03 will be utilized for dose delays. A copy of the CTCAE version 4.03 can be downloaded from the CTEP website:

http://ctep.cancer.gov/protocolDevelopment/electronic applications/ctc.htm.

For adverse events (AEs) that are considered at least partly due to administration of durvalumab or tremelimumab the following dosing guidance may be applied:

- Treat each of the toxicities with maximum supportive care (including holding the agent suspected of causing the toxicity where required).
- If the symptoms promptly resolve with supportive care, consideration should be given to continuing the same dose of durvalumab or tremelimumab along with appropriate continuing supportive care.
- The maximum amount of time that durvalumab and tremelimumab can be held before a participant is permanently withdrawn from the study is 56 days.
- In the event that the treating investigator believes a toxicity to be related to tremelimumab and not to durvalumab, the treating investigator may opt to discontinue tremelimumab and continue with durvalumab as monotherapy once the toxicity has resolved to ≤ Grade 1 or baseline. If tremelimumab is discontinued prematurely due to toxicity, it may not be reinstated.
- If tremelimumab dosing is held but toxicity does not necessitate discontinuation of the study agent, participants may receive the 4 total doses of tremelimumab (i.e. the tremelimumab infusion may be given upon acceptable resolution of the adverse event rather than omitted or skipped entirely).

In addition, there are certain circumstances in which durvalumab or tremelimumab should be permanently discontinued.

Following the first dose of durvalumab or tremelimumab, subsequent administration of durvalumab or tremelimumab can be delayed based on toxicities observed (see **Tables 3 - 6**). **Dose reductions of either durvalumab or tremelimumab are not permitted.**

Based on the mechanism of action of durvalumab or tremelimumab leading to T-cell activation and proliferation, there is the possibility of observing immune related Adverse Events (irAEs) during the conduct of this study. Potential irAEs include immune-mediated colitis, pneumonitis, hepatitis/hepatotoxicity, neuropathy/neuromuscular toxicity, endocrinopathy, dermatitis, pancreatitis and nephritis. Subjects should be monitored for signs and symptoms of irAEs. In the absence of an alternate etiology (e.g., infection or PD) signs or symptoms of colitis, pneumonitis, hepatitis/hepatotoxicity, neuropathy/neuromuscular toxicity, endocrinopathy, dermatitis, pancreatitis and nephritis should be considered to be immune-related.

Dose delay requirements and toxicity management guidelines for immune-mediated reactions, infusion-related reactions, and non-immune-mediated reactions are detailed in **Tables 3 - 6**.

In addition, reporting guidelines for adverse events of special interest (AESIs) and serious adverse events (SAEs) are detailed in Sections 7.4, 7.5, 7.9, 7.10, and 7.11.

